- By means of the revision of the daily tool of the subject.

Procedure to monitor adherence:

- The evaluation of the adherence by means of the diary of the subject will be carried out in the following way:

$$Ad = (A_r)100/A_i$$

Where:

Ad = Adherence

Ar = registered applications.

Ai = Indicated applications.

Only subjects with a minimum adherence of 80% by means of the subject's daily tool will be considered for efficacy analysis.

6.3.3 Treatments and concomitant interventions allowed and prohibited before and during the study.

The subjects admitted correctly to the study, who meet the eligibility criteria, may continue with the systemic treatment of the underlying diseases. If during the development of the study they require the implementation of a new permitted medication, they may do so. All concomitant medications used must be duly reported in the notes of the clinical file and in the corresponding section.

Allowed medications:

- Ophthalmic:

All permitted medications applied via ophthalmic during the study, must wait a minimum period of 10 minutes from the last application of the treatments under study or reference. The above in order to avoid the interaction of treatments in the tear film, based on the tear flow index and the physiological tear volume. [36]

- o Tetracaine 0.5%
- o Tropicamide 0.8% / Phenylephrine 5%

- Administered by a route other than ophthalmic:

- o Medicines whose effect may be susceptible of modifying any of the parameters of efficacy, safety or tolerability of this research protocol must notify their clinical monitor or the scientific committee of the sponsor to judge the convenience of entry, continuation or elimination of the participant according to correspond

Any medication allowed that is used, besides appearing in the clinical note, must be registered in the section of concomitant medications in the CRF.

Prohibited drugs:

- Any medication with ophthalmic application that is not on the list of allowed medications. The rest period prior to entering the study is according to the table.

Table 4. Rest period of medications with ophthalmic application.

Type of medication	Example	Rest period
Ophthalmic anti-inflammatories (Steroids and NSAIDs)	Diclofenac	48 hours
	Dexamethasone	
Ophthalmic antibiotics	Ciprofloxacin	24 hours
	Tobramycin	
Any other ophthalmic medication, including lubricants	Hipromellose	2 hours
	Timolol	

6.3.4 Treatment management.

The treatments will be provided by Sophia Laboratories, S.A. of C.V., for each research center. They will be labeled and reconciled. The handling of the treatment will be under the responsibility of the IP or a designated member of his team.

6.3.4.1 Delivery and reception.

The sponsor will be responsible for delivering the study treatments at the research center according to internal procedures. The delivery will be made in closed boxes by means of a courier service or directly by the sponsor's staff to the address of the research center according to the study plan.

The reception will be exclusively carried out by the team of the research center, by the pharmacist. You should check the good condition of the primary packaging (box). In the event that it shows alterations or defects in its integrity that from its judgment could have damaged the content, it should report it to the sponsor. If the package does not show significant defects, it will proceed to open it.

Inside you must locate the acknowledgment document and the logger (data logger) of temperature and humidity. You should check that the registered temperature and humidity comply with the specifications for transport and shelter (see 6.3.4.2 Storage). Subsequently verify the content (treatments) with what is reported in the document. In case the document corresponds to the content, it will sign the receipt and send it to the sponsor. Otherwise, notify the sponsor.

In the study center, the pharmacist will deliver the corresponding treatment to the subjects admitted. The center must register the medicine delivered.

6.3.4.2 Storage .

The medication must be stored in a secure area with restricted access. Storage should be at room temperature to no more than 30 ° Celsius.

The research center has the obligation to record, in the format designated by the sponsor, the temperature and humidity registered in the data logger. This record should include the current temperature and humidity, as well as the minimum and maximum of each of these. It must be done at least once a day, on business days.

Said data will be compared by the clinical monitor according to the registration in the data logger.

6.3.4.3 Return .

The research subjects will return, to the personnel indicated by the IP in the center, their treatments in the final visit.

The refund will be made by the research center when the sponsor indicates it. Prior to the return the research center must make a count of the assigned medication and the remaining medication, with the aim of creating an inventory which serves for the final filling of the medication return form.

6.4 Outcome variables.

6.4.1 Security variables.

- Adverse events

6.4.2 Efficacy variables.

6.4.2.1 Primary outcome variables.

- Clinical remission of acute bacterial conjunctivitis on day 8, defined by the absence of:
 - Conjunctival secretion
 - Bulbar conjunctival hyperemia.

6.4.2.2 Secondary outcome variables.

- Bacterial eradication, on day 8, in the cultures of patients with positive basal cultures. Bacterial eradication will be defined as the absence of bacterial species that were present in the culture of the baseline visit.
- Degree of conjunctival hyperemia during visits
- Degree of conjunctival secretion during visits
- Overall investigator rating of clinical changes and symptoms during visits.

6.4.3 Methods and scales to be used for the measurement of the variables.

The variables and their units of measurement are included in **Table 5 Method of measuring variables**.

Variable	Unity	Symbol	Type	Method of measurement
Overall rating	Degrees	---	C. Ordinal	Direct observation and interrogation
Bacterial eradication	Colony forming units	UFC	C. Continuous	Secretion culture
Adverse events	Number of cases	N	C. Discrete	Count
Conjunctival bulbar hyperemia	Degrees	---	C. Ordinal	Direct observation (Biomicroscopy)
Clinical referral	If not	---	Qualitative rated	Direct observation (Biomicroscopy)

Variable	Unity	Symbol	Type	Method of measurement
Conjunctival secretion	Degrees	---	C. Ordinal	Direct observation (Biomicroscopy)

Table 5 Method of measuring variables.

The following describes the methods and scales that will be used for the measurement of the variables, which are in strict alphabetical order of the procedure:

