Globally, the most common presentation of bacterial conjunctivitis is acute. Some variations in the presentation of cases of acute bacterial conjunctivitis have been described, showing a peak in the period from December to April in the northern hemisphere, corresponding to winter, while viral conjunctivitis has its peak in the summer months and conjunctivitis. allergic during the spring. [6] [7] [8] It is estimated that in developed countries, 1-4% of general medical consultations have the red eye as a reason for consultation, and that most of these are diagnosed as acute bacterial conjunctivitis. [9] [10] [11] [12] [13] In countries such as Norway, it has been suggested that in 30 out of every 1000 patients who attend a general medical consultation, there is a diagnostic impression of acute bacterial conjunctivitis, this being confirmed diagnosis in 2 of 3 cases. [5] Epidemiological data on bacterial conjunctivitis tend to differ among authors, due in large part to the fact that most cases of conjunctivitis are treated at the first level of medical care, and it has been suggested that general practitioners diagnose conjunctivitis bacterial. [5]

5.1.1 Etiology of bacterial conjunctivitis.

In healthy subjects, it is common for microorganisms to be isolated from their conjunctiva. The conjunctiva under normal circumstances presents a flora with bacterial colonization and transient or recurrent bacterial contamination. Colonization means the stable presence of microorganisms, in balance with host defense mechanisms; while the contamination represents microorganisms introduced from sources external to the conjunctiva. [14] Most of the microorganisms present, in a healthy conjunctiva, are due to transient or recurrent contamination, true colonization is more common in the palpebral margins. Given the right conditions, any microorganism can cause an

infection. A primary pathogen consistently produces infections, opportunists require that the individual's immunity be compromised, while most microorganisms act as incidental pathogens, that is, they replicate and cause disease when the host's defense mechanisms are affected they see compromised. [15]

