In samples of healthy conjunctiva, it is common to isolate coagulase-negative staphylococci and corynebacteria, and it has been reported that in normal, non-inflamed conjunctiva, coagulase-positive staphylococci, streptococci, haemophilus, moraxella, and gram-negative bacilli have also been isolated, which are organisms traditionally pathogenic [16] [17] [4]

The most frequent causative agents of bacterial conjunctivitis are: *S. aureus*, *S. epidermidis*, *H. influenzae*, *S. pneumoniae*, *S. viridians*, *Moraxella catarrhalis* and gram-negative intestinal bacteria. [4] Varying in its presentation, according to climatic, social, hygienic and age conditions.

However, several studies have shown a high frequency of negative bacteriological cultures in patients with classical symptoms of acute bacterial conjunctivitis, reporting up to 22-68% of negative cultures. [18] [19] [20] [21] The variation in this frequency, has been tried to explain by the different interpretations that the authors give the results of the cultures.

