The microbiological study of body tissue and fluid samples allows to establish the etiological diagnosis of different infectious diseases. For this reason it is important to guarantee the quality of the sample and the information that must accompany it during the process that begins in the pre-analysis phase, which includes preparation, procurement and transportation, which concludes in the analysis of the sample.

The conjunctival secretion sample will be taken prior to the instillation of any medication (eg tetracaine, tropicamide / phenylephrine) or staining (fluorescein, lysine green) required for ophthalmologic evaluation.

You will use the sample taking kit delivered by the sponsor for this purpose. The kit will consist, as a minimum, of two test tubes and two sterile swabs. Each tube will have a label with the following minimum information:

- Study number: SOPH157-0217 / III
- Initials of the subject
- Subject number
- Visit
- Right Eye or Left Eye (as the case may be)

Use gloves for this procedure. Take a sample with the swab, use a swab per eye. Rotate the swab in the conjunctival cul-de-sac while moving it from the medial to the lateral zone (see Illustration 2). Place the swab in the transport medium (sterile tube with screw cap or rubber stopper). Fill in the required information on the label of each tube. And perform the same procedure on the contralateral eye.

[figure not shown]

Illustration 2. Conjunctival secretion sampling.

Fill the requisition form delivered by the sponsor and contact the authorized third party for the analysis of the samples, to schedule the collection. The sample should be kept at room temperature.

In the CRF it will register as done, in each one of the eyes. The results will be delivered by the third party authorized to the IP and the sponsor.

Once the result of the basal crop has been obtained, the center will register this result in the CRF. When you obtain the results of the final crop you will register them in the CRF. And it will mark in the box of the CRF the question ¿Bacterial Eradication? If not. The absence of bacterial species that were present in the culture of the baseline visit is considered bacterial eradication.

The authorized third party will be selected by the sponsor and the relevant information will be shared with the centers, which will be in the master folder of the study.

6.4.4 Time of the measurement of variables.

- **Measurements in the baseline visit**

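### Bacterial eradication is scored on every species grown at baseline, with no pathogen list, count threshold or definition of a positive culture, so persisting or transient normal flora can decide the result

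*Combined protocol and SAP*

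**What the plan says.** Section 6.4.2.2 sets the analysis set and the outcome. The endpoint is "Bacterial eradication, on day 8, in the cultures of patients with positive basal cultures", followed by "Bacterial eradication will be defined as the absence of bacterial species that were present in the culture of the baseline visit". Section 6.4.3.4 gives sites the same rule for the Yes/No box in the CRF: "The absence of bacterial species that were present in the culture of the baseline visit is considered bacterial eradication". Both eyes are swabbed, an authorized third party does the analysis, and the site enters the result. No criterion for reading the culture is stated.

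Table 5 in section 6.4.3 lists the unit of bacterial eradication as "Colony forming units" and its type as continuous, but no count enters the definition.

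The background in section 5.1.1 bears directly on the rule. It says "In healthy subjects, it is common for microorganisms to be isolated from their conjunctiva" and, more specifically, "In samples of healthy conjunctiva, it is common to isolate coagulase-negative staphylococci and corynebacteria". It adds that "in normal, non-inflamed conjunctiva, coagulase-positive staphylococci, streptococci, haemophilus, moraxella, and gram-negative bacilli have also been isolated". Its list of the usual causes of infection, which starts "The most frequent causative agents of bacterial conjunctivitis are", includes S. epidermidis, itself a coagulase-negative staphylococcus. None of this is carried into the endpoint definition.

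**The concern.** The endpoint is meant to show whether the infecting organism was removed. As written, it asks whether every species on the baseline plate is gone on day 8. The protocol's own background says some of those species may be ordinary residents of a healthy eye, so the result can turn on carriage and not on infection.

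This is the only microbiological endpoint in the trial, and section 5.4 relies on culture to support the diagnosis. Misclassification unrelated to treatment tends to make two arms look alike. In a non-inferiority trial that is the unhelpful direction, because a real deficit in eradication would look smaller than it is. Choosing a species or threshold rule after results are known would be open to challenge.

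**Working it through.** The documents give no eradication rate, power or threshold for this endpoint, so there is no plan figure to reproduce. The check sets the rule against the background text and then illustrates size with assumed rates.

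**Step 1. Apply the rule literally.**

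| Baseline growth | Day 8 growth | Score under 6.4.2.2 | Depends on how positive is defined? |
|---|---|---|---|
| Pathogen plus corynebacterium | Corynebacterium only | Failure | No: the pathogen already makes the culture positive |
| Transient contaminant only | None | Success | Yes |
| Commensal only | Same commensal | Failure | Yes |

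The first row follows from the stated rule under any reading of a positive culture. The other two arise only if commensal or contaminant growth alone counts as positive.

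**Step 2. Commensal-only cultures (all rates assumed).** Let f be the share of positive cultures that are commensal only, P the true pathogen eradication rate and C the commensal clearance rate.

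Observed rate = (1 − f) × P + f × C.

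With P = 80% and 95% in the two arms and C = 50% in both:

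| f | Arm with P = 80% | Arm with P = 95% | Difference (points) |
|---|---|---|---|
| 0% | 80.0% | 95.0% | 15.0 |
| 10% | 77.0% | 90.5% | 13.5 |
| 20% | 74.0% | 86.0% | 12.0 |
| 30% | 71.0% | 81.5% | 10.5 |
| 40% | 68.0% | 77.0% | 9.0 |

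With equal C in both arms, the difference is (1 − f) × 15 whatever the value of C. With unequal C, a term f × (difference in C) is added. At f = 25%, a 15-point difference in C in the same direction gives 0.75 × 15 + 0.25 × 15 = 15, so there is no shrinkage.

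The rate itself moves by f × (C − P), which can have either sign. At P = 75% and f = 25%:
- C = 40% gives 0.75 × 0.75 + 0.25 × 0.40 = 66.3%, a fall.
- C = 90% gives 0.75 × 0.75 + 0.25 × 0.90 = 78.8%, a rise.

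**Step 3. Mixed cultures (all rates assumed).** Let m be the share of pathogen-positive cultures that also grow a commensal, and q the chance that it persists, independently of the pathogen.

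Observed rate = P × (1 − m × q).

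At P = 90%, m = 25% and q = 30%: 0.90 × (1 − 0.075) = 83.3%. Over m from 10% to 50% and q from 10% to 60%, the result runs from 0.90 × 0.99 = 89.1% down to 0.90 × 0.70 = 63.0%.

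With the same m and q in a second arm at P = 75%, the observed rate is 0.75 × 0.925 = 69.4%. A true 15-point difference then shows as 83.3 − 69.4 = 13.9 points.

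**The case against.** The best defence is that the plan never says any growth is positive. It refers only to positive cultures, and the laboratory may use its own criterion in papers held in the master folder. That defence stands in part. A reader might infer that every patient with any growth enters the set, but the documents do not say so. It does not rescue the mixed culture in the first row of Step 1, where the stated rule scores a persisting commensal as failure whatever made the culture positive.

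Three other tempting readings also go too far:

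- **That the rule lowers the eradication rate.** Persisting commensals lower it, while vanishing contaminants can raise it. The net sign is unknown.
- **That 51 to 125 patients are affected.** These figures come from applying the 22–68% negative-culture range in section 5.1.1 to 160 patients: 160 × 0.32 = 51 and 160 × 0.78 = 125. That section links the spread to differing interpretations of cultures, and nothing shows that those studies used an any-growth rule. The efficacy set is also narrowed by 80% adherence (section 6.3.2) and by the need for baseline and final measurements (section 8.3.3).
- **That isolates of normal-flora species carry no information.** S. epidermidis is on the causative list, and section 5.2 cites quinolone resistance in methicillin-resistant strains of it as a reason to develop the product. It needs a threshold, not exclusion.

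A fair criticism of any remedy is that species and counts cannot fully separate carriage from infection, since section 5.1.1 reports traditional pathogens in non-inflamed eyes. That stands and limits what the fix can claim.

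**Conclusion.** The concern holds for this secondary endpoint. The stated rule can misclassify patients in both directions on the protocol's own account of normal flora, and the missing definition of a positive culture widens the problem.

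The size cannot be fixed from the documents. The shrinkage from 15 to between 13.5 and 9 points rests on assumed eradication rates, an assumed commensal-only share of 10% to 40% and equal commensal clearance in the two arms. If clearance differs between arms, the shrinkage may be smaller or absent.

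A reader might infer that the trial's main conclusion is at risk. It is not: the non-inferiority hypothesis in section 5.5.4 rests on clinical remission, which uses no culture result. The change is worth making because it is cheap and carries weight only if made before results are seen.

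**What to change.** In sections 6.4.2.2 and 6.4.3.4, before the first patient:

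1. Agree with the laboratory a species table with a qualifying baseline growth threshold for each species. Set a higher threshold for corynebacteria and for coagulase-negative staphylococci, including S. epidermidis. Include a default rule for unlisted species.
2. Define a positive baseline culture as at least one qualifying species in the study eye. Section 8.3.1 already takes one eye as the efficacy case, but the CRF eradication question does not say which eye it concerns.
3. Define eradication as absence on day 8 of every species that qualified at baseline.
4. Keep the any-species rule as a sensitivity analysis.
5. Confirm that the laboratory reports species-level CFU. Table 5 names that unit, but section 6.4.3.4 describes only a swab in transport medium and a Yes/No entry. If counts are not available, use a prespecified pathogen list with semi-quantitative growth, applied blind to treatment.

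The cost is one short table, a check with the laboratory and a somewhat smaller culture-positive set. Some misclassification remains: pathogens can be carried in a normal eye, and a species above threshold at baseline but at ordinary carriage level on day 8 still counts as failure.

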6.4.3.1 Biomicroscopy

It is the procedure by which, with the use of the slit lamp or biomicroscope, the ocular structures are evaluated thanks to the characteristics of the light source and the optical power of the instrument. A full assessment of the previous segment will be made, which will be recorded in the clinical file.

By means of biomicroscopy **bulbar conjunctival hyperemia, conjunctival secretion will be evaluated and will serve for the evaluation of adverse events and the global qualification.**

Conjunctival hyperemia is defined as the simplest reaction of the conjunctiva to a stimulus, a red appearance secondary to the vasodilation of the conjunctival vessels of variable intensity. He will graduate using the Efron scale. [37] The number will be reported in the CRF, according to the rating granted, in each of the visits. (See Illustration 1)

Illustration 1. Efron scale for conjunctival hyperemia.

The ocular secretion will be classified as 0 = absent, 1 = mild, 2 = moderate and 3 = severe. The number will be reported in the CRF, according to the rating granted in each of the visits.

The clinical remission in the visits will be evaluated as "Yes" or "No", to report "Yes" it must have a grade of "0" in conjunctival hyperemia and "0" in secretion; otherwise, you must report as "No".

6.4.3.2 Global qualification of the investigator.

The global qualification of the investigator constitutes the integral judgment of the clinical picture of the subject, including signs and symptoms, after a routine ophthalmological evaluation and interrogation. It will be classified 0 = cure, 1 = improvement, 2 = no changes compared to before starting treatment, 3 = worsened. It will be registered in the CRF in each of the follow-up visits.

6.4.3.3 Evaluation of adverse events.

The evaluation of adverse events requires a questioning conducted by the IP and the appropriate exploratory techniques for its detection.

The IP will register in the corresponding section of the CRF the EA that the subjects of the study will present.

The management of the EAs will be done according to what is described in section 9.3 Adverse events.

6.4.3.4 Sampling of conjunctival secretion for bacterial culture.

The microbiological study of body tissue and fluid samples allows to establish the etiological diagnosis of different infectious diseases. For this reason it is important to guarantee the quality of the sample and the information that must accompany it during the process that begins in the pre-analysis phase, which includes preparation, procurement and transportation, which concludes in the analysis of the sample.

The conjunctival secretion sample will be taken prior to the instillation of any medication (eg tetracaine, tropicamide / phenylephrine) or staining (fluorescein, lysine green) required for ophthalmologic evaluation.

You will use the sample taking kit delivered by the sponsor for this purpose. The kit will consist, as a minimum, of two test tubes and two sterile swabs. Each tube will have a label with the following minimum information:

- Study number: SOPH157-0217 / III
- Initials of the subject
- Subject number
- Visit
- Right Eye or Left Eye (as the case may be)

Use gloves for this procedure. Take a sample with the swab, use a swab per eye. Rotate the swab in the conjunctival cul-de-sac while moving it from the medial to the lateral zone (see Illustration 2). Place the swab in the transport medium (sterile tube with screw cap or rubber stopper). Fill in the required information on the label of each tube. And perform the same procedure on the contralateral eye.

[figure not shown]

Illustration 2. Conjunctival secretion sampling.

Fill the requisition form delivered by the sponsor and contact the authorized third party for the analysis of the samples, to schedule the collection. The sample should be kept at room temperature.

In the CRF it will register as done, in each one of the eyes. The results will be delivered by the third party authorized to the IP and the sponsor.

Once the result of the basal crop has been obtained, the center will register this result in the CRF. When you obtain the results of the final crop you will register them in the CRF. And it will mark in the box of the CRF the question ¿Bacterial Eradication? If not. The absence of bacterial species that were present in the culture of the baseline visit is considered bacterial eradication.

The authorized third party will be selected by the sponsor and the relevant information will be shared with the centers, which will be in the master folder of the study.

6.4.4 Time of the measurement of variables.

- **Measurements in the baseline visit**
- Bulbar conjunctival hyperemia
- Conjunctival secretion
- Sampling of conjunctival secretion
- **Measurements in visit 1**
- Overall rating
- Adverse events
- Bulbar conjunctival hyperemia
- Clinical referral
- Conjunctival secretion
- **Final visit measurements**
- Overall rating
- Adverse events
- Bulbar conjunctival hyperemia
- Clinical referral
- Conjunctival secretion
- Sampling of conjunctival secretion
- **Security call measurements**
- Evaluation of adverse events

6.5 Schedule and study diagram.

The **baseline visit** will be considered on day 1 of the study, the IP will indicate the subject to start the application of the products under investigation that same day. If necessary, adjust the scheme so that it complies with the 3 applications of day 1; nevertheless, in the event that during the opening hours it is not feasible to adjust the 3 applications, the IP will indicate the application of at least 2 instillations, with a minimum of 3 hours between them.

Visit 1 will be performed in relation to the start of treatment on day 5 with a window period of ± 1 day. The **final visit** will be made on day 8, with a window period of $+ 1$ day. The **security call** will be made on day 15, with a window period of ± 2 days.

